Parts B, C, and D: All subjects will be followed for 8 weeks after study drug administration. Subjects with > 2-fold HBsAg reduction at Week 8 will undergo extended follow-up for up to 40 weeks total or until the reduction in HBsAg is < 2-fold relative to baseline at 2 consecutive collections, whichever occurs first. The extended follow-up may be discontinued at the Sponsor's discretion based on emerging data.

Study Design

This study is designed to evaluate the safety, tolerability, PK, and antiviral activity of VIR-3434.

A Safety Review Committee (SRC) will perform ongoing reviews of safety, tolerability, and antiviral activity data (Parts B and C only) at specified timepoints based on available data collected throughout the study. While the primary data that will be reviewed by the SRC for dose escalations and enrollment

of optional cohorts is listed throughout the protocol, additional relevant data from other cohorts may also be reviewed by the SRC to inform decisions. Details are provided in the SRC charter.

The study will be conducted in 4 Parts:

- **Part A:** Randomized, double-blind, placebo-controlled, single ascending dose (SAD) study of VIR-3434 administered via subcutaneous (SC) injection or intravenous (IV) infusion to healthy adult subjects
- **Part B:** Randomized, double-blind, placebo-controlled, SAD study of VIR-3434 administered via SC injection to adult subjects with chronic HBV infection without cirrhosis who are on NRTI therapy, are HBeAg-negative, and have HBsAg < 3,000 IU/mL
- **Part C:** Optional, randomized, double-blind, placebo-controlled, SAD study of VIR-3434 administered via SC injection to adult subjects with chronic HBV infection without cirrhosis who are on NRTI therapy, are HBeAg-negative or HBeAg positive, and who have HBsAg \geq 3,000 IU/mL
- **Part D:** Optional, randomized, double-blind, placebo-controlled, SAD study of VIR-3434 administered via SC injection to adult subjects with chronic HBV infection without cirrhosis who are not on NRTI therapy, have HBV DNA \geq 1,000 IU/mL, are HBeAg-negative or HBeAg positive, and have any HBsAg level

Part A

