Adult subjects with HBeAg-negative chronic HBV infection without cirrhosis and with HBsAg < 3,000 IU/mL on NRTI therapy for ≥ 2 months will be enrolled in 1 of 7 cohorts (5 planned, 2 optional) in Part B. Subject screening will occur no more than 6 weeks prior to the Day 1 visit. Subjects may be admitted into the clinical investigative site on Day -1 or 1. Prior to study drug administration on Day 1, subject eligibility will be confirmed. Any changes to medical history will also be evaluated and recorded. Eligible subjects in each cohort will be randomized to receive VIR-3434 or placebo within 48 hours prior to study drug administration on Day 1.

At the start of each cohort, 2 sentinel subjects will be randomized 1:1 to VIR-3434 or placebo. These subjects will be dosed and monitored through at least 72 hours post-dose; if the investigator(s) have no safety concerns, the remainder of the subjects in the same cohort will be dosed. Vital signs, symptom-directed physical examination(s), and AEs will be reviewed by the investigator prior to dosing any additional subjects. The remaining subjects in the cohort will be randomized 5:1 to receive a single dose of VIR-3434 or placebo. All subjects will be closely

monitored following dose administration. In the event of an acute immune reaction (such as anaphylaxis or cytokine release syndrome) recommended therapeutic and supportive measures can be found in [Appendix 8](#).

Patients must be monitored through at least 6 hours post-dose prior to discharge. Subjects will be discharged after all study assessments are performed on Day 1. All subjects will return to the clinical investigative site per the schedule of assessments ([Appendix 3](#)) through the final required follow-up day (Week 8). In the event of suspected immune complex disease, recommended therapeutic and supportive measures can be found in [Appendix 8](#). Subjects with > 2-fold HBsAg reduction at Week 8 will be followed for an additional 32 weeks or until the reduction in HBsAg is < 2-fold relative to baseline at 2 consecutive collections, whichever occurs first. During this extended follow-up period, subjects will return to the clinical investigative site for assessments per the schedule of assessments ([Appendix 3](#)). Extended follow-up may be discontinued for any subject at Sponsor's discretion based on emerging data.

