APPENDIX 6. PARTS B, C, AND D PHARMACOKINETIC TIMEPOINTS

Study Day \pm window in days (Study Week)	Protocol Time	Blood PK (serum)
Day 1	Predose (-1 h)	X
	Dose	
	1 hour (± 5 min)	X
	4 hours (± 30 min)	X
	6 hours (± 30 min)	X
Day 2	24 hours (± 2 h)	X
Day 4 + 1		X
Day 8 \pm 1 (Week 1)		X
Day 11 \pm 1		X
Day 15 \pm 2 (Week 2)		X
Day 29 \pm 2 (Week 4)		X
Day 57 \pm 7 (Week 8)		X
Day 85 \pm 7 (Week 12)		X
Day 113 \pm 7 (Week 16)		X
Day 169 \pm 7 (Week 24)		X
Day 225 \pm 7 (Week 32)		X
Day 281 \pm 7 (Week 40)		X

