6.5.1. PK Variables

PK variables include individual concentration measurements for VIR-3434 following the collection times provided in the study protocol, and the estimated PK parameters in evaluation of PK objectives including but not be limited to:

	PK Parameters
Part A	C_{max} , C_{last} , T_{max} , T_{last} , AUC_{inf} , AUC_{last} , $\%AUC_{exp}$, $t_{1/2}$, λ_z , V_z (IV only), CL (IV only), V_z/F (SC only), and CL/F (SC only)

Part B, C, and D	C_{max} , C_{last} , T_{max} , T_{last} , AUC_{inf} , AUC_{last} , $\%AUC_{exp}$, $t_{1/2}$, λ_z , V_z/F , and CL/F
------------------	---

Definition of selected PK parameters:

Symbol	Definition
C_{max}	Maximum observed concentration of drug following a dose
C_{last}	Last measurable observed concentration of drug following a dose
T_{max}	Time at which maximum concentration of drug is observed
T_{last}	Time at which last measurable concentration of drug is observed
AUC_{last}	Area under the concentration-time curve from time “0” to the last measured timepoint
AUC_{inf}	Area under the concentration-time curve from time “0” to time infinity
$\%AUC_{exp}$	Percent of the area under the concentration-time curve extrapolated from the last measured timepoint to time infinity
$t_{1/2}$	Terminal elimination half-life
λ_z	Terminal elimination rate constant
V_z	Volume of distribution during the terminal elimination phase
CL	Total body clearance
V_z/F	Apparent volume of distribution during the terminal elimination phase, measured after extravascular dosing
CL/F	Total body clearance measured after extravascular administration

The apparent terminal-phase elimination rate constant (λ_z) will be estimated by log-linear regression of the concentration-time data associated with this phase. The decision as to which data points describe the terminal elimination phase will be reached by inspecting the semilogarithmic plot of the data, only considering concentrations at time points beyond T_{max} . λ_z is considered to be well-estimated if a minimum of three data points is used, these data points cover a time span of 2 or more elimination half-lives, and the r^2 value of λ_z is ≥ 0.80 . In cases where λ_z is poorly estimated (i.e., a span of < 2 half-lives or $r^2 < 0.80$), λ_z and the related parameters (AUC_{inf} , CL/F , V_z/F , and $t_{1/2}$) will be flagged in the report and may be excluded from the calculation of summary statistics at the discretion of the clinical pharmacologist.

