AUC will be computed using the linear up, log down trapezoidal rule. AUC_{inf} is considered to be well-estimated if $\%AUC_{exp} \leq 20\%$. In cases where $\%AUC_{exp} > 20\%$, AUC_{inf} and the related parameters CL/F and V_z/F will be presented in listings but may be excluded from the calculation of summary statistics at the discretion of the clinical pharmacologist. The nominal time point for a key event or dosing interval (τ) may be used to permit direct calculation of AUC over specific

time intervals. The appropriateness of this approach will be assessed by the clinic pharmacologist on a profile-by-profile basis.

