6.5.3. Analysis of PK Parameters

PK parameter data summaries will include all participants for whom PK parameters can be derived. The sample size for each PK parameter will be based on the number of participants with non-missing data for that PK parameter.

Individual participant PK parameters for VIR-3434 will be listed and summarized using descriptive statistics (n, mean, SD, CV%, median, min, max, geometric mean, and GeoCV%). Selected summary statistics (e.g., mean with %CV or median with Q1 and Q3) of PK parameters will also be presented by treatment cohort, for Part A and Part B, C, and D.

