Notes: 
¹ Visit name for analysis purpose is used to report data in tables and figures.
 
² The analysis visit windows will be applied using the following rules for both scheduled and unscheduled visits:
 
 a. If no numerical measurement is available within a visit window, the measurement will be considered missing for the visit. b. If there is more than 1 numerical measurement available within a visit window, use the following rules: 
 i. If the scheduled visit measurement will be used if it is available ii. If not, the unscheduled visit measurement closest to the target day will be used; or iii. If there are multiple unscheduled visit measurements with the same distance from the target day, the latest measurement will be used. 
³ For an assessment, e.g., laboratory, ECG and vital sign measurement collected on the date of first dose of study drug, if it cannot be determined whether the measurement is before or after the first dose:
 
 a. Scheduled measurement will be treated as pre-dose observation. b. Unscheduled measurement will be treated as post-dose observation. 
⁴ For vital signs, Day 1 will be included in the Day 1 visit window to account for the post-dose assessments on Day 1, .
 
⁵ PK analysis window will follow the protocol-defined assessment visit window.
			

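### In Parts B–D the end of the AUClast interval depends on HBsAg response, yet AUClast is summarised by cohort and no common-interval AUC is committed to

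*SAP*

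**What the plan says.** **Who is sampled, and for how long.** All Parts B–D subjects are followed for 8 weeks. The Protocol synopsis (Duration of Follow-Up) then states: "Subjects with > 2-fold HBsAg reduction at Week 8 will undergo extended follow-up for up to 40 weeks total". Follow-up stops sooner if the reduction is below 2-fold at two consecutive collections. Protocol 5.1.2 to 5.1.4 add a second exit: "Extended follow-up may be discontinued for any subject at" the sponsor's discretion. The PK samples at Weeks 12, 16, 24, 32 and 40 (Protocol Appendix 6; Appendix 3 schedule) all fall in this extended period. Part A has no such gate; everyone is followed for 24 weeks.

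**What is computed.** AUClast is a named secondary-endpoint parameter for Parts B–D. SAP 6.5.1 runs it from time zero "to the last measured timepoint", which is each subject's own. SAP 6.5 presents PK by cohort, and SAP 6.5.3 says "PK parameter data summaries will include all participants for whom PK parameters can be derived". SAP Appendix 2, note 5, sets no Week 8 cut: "PK analysis window will follow the protocol-defined assessment visit window". By contrast, the antiviral and ADA visit summaries (SAP 6.7.2, 6.6.2) stop at Week 8 in these Parts.

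**What is allowed instead.** SAP 6.5.1 says nominal times "may be used to permit direct calculation of AUC over specific" intervals, then adds: "The appropriateness of this approach will be assessed by the clinic pharmacologist on a profile-by-profile basis". SAP 6.5.4 names AUClast and/or AUC0-t as the dose-proportionality fallback when AUCinf is poorly estimated. It does not define t.

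**The concern.** Integration time is set by a pharmacodynamic outcome. Two subjects with identical concentrations receive different AUClast values because one responded and was sampled longer. A cohort geometric mean or geometric CV of AUClast then mixes exposure with the share of subjects extended, and that share may differ between doses and between Parts.

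Protocol 10.5 also commits to relating PK parameters to antiviral variables. If AUClast were the exposure used, response would lengthen the exposure interval and create an association by design.

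The permitted interval AUC does not close the gap. A decision taken profile by profile cannot guarantee one interval within a cohort.

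**Working it through.** **1. Reproduce the plan's half-life.** Inputs (Protocol 2.3.2): CL 0.0657 L/day, V1 2.43 L, Q 0.6127 L/day, V2 2.85 L.

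- k10 = 0.0657/2.43 = 0.0270; k12 = 0.6127/2.43 = 0.2521; k21 = 0.6127/2.85 = 0.2150; sum s = 0.4942.
- β = [s − √(s² − 4·k10·k21)]/2 = 0.01206 per day.
- t½ = ln 2/β = 57.5 days, against about 58 stated.

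**2. AUClast ratio for identical PK.** Assumptions: first-order SC absorption with ka 0.1 to 0.5 per day (not in the documents; bioavailability cancels), and all samples quantifiable. The concentration is a sum of three exponentials with rates α, β and ka, so AUC(0–t) = Σ coefficient × (1 − e^(−rate·t))/rate. Week 8, 16 and 40 are 56, 112 and 280 days after dosing. Patient half-life is not given, so CL is multiplied by 1, 2, 3 and 5 to cover faster elimination.

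| CL multiple | t½ (days) | Week 16 / Week 8 | Week 40 / Week 8 |
|---|---|---|---|
| 1 | 57.5 | 1.50–1.62 | 1.95–2.19 |
| 2 | 29.7 | 1.26–1.36 | 1.36–1.49 |
| 3 | 20.4 | 1.14–1.22 | 1.17–1.25 |
| 5 | 13.1 | 1.05–1.09 | 1.05–1.10 |

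Week 16 is the earliest exit through two consecutive scheduled collections (Weeks 12 and 16).

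**3. Effect on a cohort of 6 active subjects, 3 extended.** With ratio R, the geometric mean is multiplied by R^(1/2). The log variance is ln(1 + 0.30²) = 0.0862 for an assumed true GeoCV of 30%, plus 0.25 × (ln R)² × 6/5. The SAP 6.5.2 formula then gives the reported GeoCV.

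- t½ 57.5 days, extension ending at Week 16: geometric mean ×1.23–1.27, GeoCV 38–41%.
- t½ 57.5 days, to Week 40: ×1.40–1.48, GeoCV 50–56%. For example, R = 2.19 gives an added variance of 0.184 and √(e^0.2706 − 1) = 56%.
- To Week 40 at 29.7, 20.4 and 13.1 days: ×1.17–1.22, ×1.08–1.12 and ×1.03–1.05; GeoCV 35–38%, 31–33% and 30–31%.

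**4. Does AUCinf avoid the problem?** Not at the predicted half-life. SAP 6.5.1 asks the λz points to span 2 half-lives, which is 2 × 57.5 = 115 days; a subject stopped at Week 8 has 56. By day 56 the model has accrued 44–50% of AUCinf, so 50–56% is extrapolated against a limit of 20%. At 29.7 days it still fails (59 days needed, 27–33% extrapolated).

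**5. Dose-proportionality slope, if evaluated in Part B** (6, 18, 75, 300 mg; true slope 1.00; t½ 57.5 days). Slope = 1 + least-squares slope of (fraction extended × ln R) on ln dose.

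- Equal extension at all doses: 1.00.
- Graded extension (2, 3, 4, 5 of 6): 1.05–1.10 for extension ending at Week 16 to Week 40.
- None below 75 mg and all from 75 mg up: at most 1.24.

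Expected 90% CIs for extension to Week 40 (6 active per dose, 22 df, between-subject CV 30–50%) lie within 0.95–1.24 (graded) and 1.09–1.36 (all-or-none). All are inside the SAP's (0.7, 1.43).

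**The case against.** **The study is exploratory.** It has no hypotheses, PK is secondary, and dose proportionality in Parts B–D is optional. Tlast, %AUCexp, individual values and the number quantifiable per timepoint are all shown, so a reader can see unequal follow-up. This stands and limits the severity. It does not make a cohort mean comparable, because visibility is not correction.

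**The largest figures are upper-end ones.** The 58-day half-life is a linear prediction scaled from monkeys and used to simulate Part A, where HBsAg is absent. Target binding may shorten it. At 20 days or less the distortion is modest, and if profiles are below quantification by about Week 8 there is little effect. Extension may also end well before Week 40. This stands too, hence the ranges above.

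**The SAP already allows an interval AUC.** True, and a reader should not infer that a common-interval AUC is ruled out. The gap is that t is undefined and nothing commits to its use.

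**Two stronger readings are not supported.** A reader might infer that the dose-proportionality conclusion would be wrong. The slope moves only if extension rises with dose, and no computed interval leaves the acceptance range. A reader might also infer that the exposure-response analysis is circular. Protocol 10.5 names no exposure metric and defers to the SAP, whose visible text names none; parts of the SAP are redacted, so this stays conditional.

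**Conclusion.** The concern holds in limited form. Following the plan as written gives Parts B–D cohort AUClast summaries that depend partly on HBsAg response. For identical PK the difference is about 2-fold at the predicted half-life with extension to Week 40, falling to 5–10% at 13 days. These figures rest on the protocol's linear model, the assumed ka and quantifiable samples; patient half-life, assay LLOQ and extension rates are not given. No hypothesis test or sample size is affected. It should be fixed, because the descriptive comparison is otherwise hard to interpret and the change is cheap.

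**What to change.** In SAP 6.5.1, 6.5.3 and 6.5.4, for Parts B–D:

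- Define t in AUC0-t as 56 days after dosing (nominal Week 8). Prespecify AUC(0–56d), for free and total PK where each is measured, as the AUC for cohort comparisons, any dose-proportionality analysis and exposure-response.
- **Week 8 sample off-day:** log-linear interpolation or short extrapolation to day 56. **Week 8 missed but a later sample exists:** log-interpolate. In the same linear model these rules err by at most 0.34% and 0.8%; leaving the ±7-day window uncorrected errs by about 2–11%.
- **Last sample still quantifiable, taken before Day 50, none later:** not evaluable; listed but not summarised.
- **Profile below quantification before or at Week 8:** use the area to the last quantifiable sample, flagged and counted. As a sensitivity analysis, add a log-linear segment from that sample to LLOQ at the first BQL time. The omitted area cannot be taken as at most LLOQ × remaining days. With Day 29 at 10 × LLOQ and decline to LLOQ at Day 57, it is (10 − 1)/ln 10 = 3.9 times that amount.
- Keep AUClast summarised, as Protocol 10.5 requires, but beside Tlast and the number in extended follow-up, and not as the between-cohort exposure measure.

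The cost is SAP wording and one partial-AUC definition in the NCA software; no new samples are needed. The downside is that AUC(0–56d) captures only about 44–50% of AUCinf at the predicted half-life, and early leavers drop out of its summary.

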6.5.2. Analysis of PK Concentrations

Individual serum concentrations of VIR-3434 will be listed and summarized by nominal sampling time using descriptive statistics (n, mean, SD, coefficient of variation [CV%], median, min, max, geometric mean, and geometric CV% [GeoCV%]). Geometric CV% will be calculated using the following formula where SD is the standard deviation of the log-transformed data:
$$\text{GeoCV\%} = \sqrt{(\exp(\text{SD}^2) - 1)} \times 100.$$

An individual participant listing including actual sampling date and time and elapsed time relative to dosing time will be provided by study part, treatment cohort, subject ID, and nominal sampling time, with time deviation (difference in minutes between nominal and actual sampling times) calculated, for participants with available concentration data.

Anomalous concentrations identified as sampling errors by the clinical pharmacologist will be excluded from summaries but flagged in the listings.

Individual and aggregate mean (\pm SD) of serum VIR-3434 free and total concentrations data (as applicable) will be displayed graphically in linear and semi-logarithmic plots of concentration versus time by treatment cohort, for Part A and Part B, C, and D. Time will be displayed in units of days of time elapsed relative to dosing, with dosing at time zero (clinical Day 1). The nominal sample collection timepoints will be used for plots of mean concentrations. The number of participants with quantifiable concentrations per timepoint will be displayed in each plot. Mean postdose concentration values that are BQL will not be displayed in the figures and remaining points connected. Natural logarithm transformation will be used for serum concentrations.

6.5.3. Analysis of PK Parameters

PK parameter data summaries will include all participants for whom PK parameters can be derived. The sample size for each PK parameter will be based on the number of participants with non-missing data for that PK parameter.

Individual participant PK parameters for VIR-3434 will be listed and summarized using descriptive statistics (n, mean, SD, CV%, median, min, max, geometric mean, and GeoCV%). Selected summary statistics (e.g., mean with %CV or median with Q1 and Q3) of PK parameters will also be presented by treatment cohort, for Part A and Part B, C, and D.

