5.5. Replacement of Subjects

Subjects who do not receive the full planned dose or discontinue due to an AE that does not meet cohort stopping criteria (Section 5.6) may be replaced with confirmation by the SRC. Subjects who discontinue from the study for non-safety-related reasons or for reasons other than those requiring SRC confirmation (listed above) may be replaced following discussion between the Sponsor Medical Monitor (or designee) and the investigator.

The replacement subject will be assigned a unique subject identification number and will receive the same study drug assignment and dose level as the subject who is being replaced and in the same blinded fashion.

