5.2. Full Analysis Set

The Full Analysis Set (FAS) includes all randomized participants who received at least 1 dose of study drug. The FAS will be used to summarize participant demographics and baseline characteristics, and analysis for antiviral activity endpoints, unless otherwise specified.

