5.4. PK Analysis Set

The PK Analysis Set includes all participants in the FAS with at least 1 measurable postdose concentration data to provide interpretable results. The PK Analysis Set will be used for all PK analyses.

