6.4. Safety Analyses

Safety analyses will be based on data from the TE Period for all participants in the Safety Analysis Set, unless otherwise specified. All safety data will be included in the individual participant listings. Participants will be analyzed according to the treatment dose level they received.

The overall safety profile of the study intervention will be assessed in terms of the following safety and tolerability assessments:

- TEAEs
- Clinical laboratory
- ECG
- Vital signs
- Physical examination

Only descriptive analysis of safety will be performed, and no statistical testing will be performed.

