6.5. Pharmacokinetics Analysis

All analyses and summaries of PK serum concentrations and PK parameters will be based on the PK Analysis Set and presented by VIR-3434 treatment cohort and placebo, for each of Part A, B, C, and D. Blood samples of VIR-3434 will be obtained from each participant prior to study drug administration and at selected times after study drug administration as outlined in the study protocol.

Standard non-compartmental methods will be used to estimate PK parameters based on VIR-3434 concentration data using Phoenix WinNonlin® software (Version 8.3.5 or higher). The linear/log trapezoidal rule will be used in conjunction with dosing time, serum concentration, and corresponding real-time values. If the real sampling time will not be recorded or will be missing, the planned time will be used for this time point instead.

For concentration data, values reported below the quantitation limit (BQL) will not be imputed in summary statistics with only the number of participants who have non-missing quantifiable results included at each time point.

For estimation of PK parameters, samples BQL prior to the first quantifiable concentration will be set to a concentration value of zero, and BQL values that occur after the first quantifiable point will be considered as missing data.

If a missing value is reported due to no valid or missing of sample result in summary of concentration data and PK parameters, it will be presented as not reported “NR” and excluded from PK analyses and not imputed at any time points. The actual reported values will be provided in individual participant listings.

Natural logarithm transformation may be used for analysis of PK parameters. PK parameters that are BQL will be imputed before log transformation or statistical model fitting. If untransformed value is BQL, the corresponding log transformed value will be zero.

The precision of data reporting in both PK concentrations and PK parameters will follow the below rules:

- 3 significant figures in the same units as the laboratory source data in ng/mL
- 3 significant figures for descriptive statistics except for
 - 4 significant figures for standard deviation
 - percentage to 1 decimal place for CV% and Geometric CV%

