6.5.4. Analysis of Dose Proportionality for PK parameters

Dose proportionality will be evaluated for healthy subjects in Part A who were administered VIR-3434 SC. Dose proportionality may also be evaluated for participants in Part B, C, and D. PK parameters from subjects with dosing deviation will be excluded from the analysis.

To assess dose proportionality, the natural log transformed PK parameters, including AUC_{inf} (AUC_{last} and/or AUC_{0-t} will be used if AUC_{inf} is poorly estimated) and C_{max} , will be analyzed using power model [1], with VIR-3434 log transformed dose level as the independent variable, in form of $\ln(y) = \beta_0 + \beta_1 * \ln(\text{VIR-3434 dose})$, where y = the PK parameter of interest.

Dose proportionality is concluded if 90% CI for the β_1 falls within the critical interval of (0.7, 1.43), which is less than 30% difference between doses for a given PK parameter.

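### A part-dosed subject is left out of the dose-proportionality model but stays in the cohort exposure summaries, because SAP 6.5.2 and 6.5.3 have no rule for dosing deviations

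*SAP*

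**What the plan says.** The inclusion rule for the cohort tables is in SAP 6.5.3: "PK parameter data summaries will include all participants for whom PK parameters can be derived". The next section, SAP 6.5.4, has a different rule for the power model: "PK parameters from subjects with dosing deviation will be excluded from the analysis". That model is planned for Part A subjects dosed SC and may also be run for Parts B, C and D.

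The sets behind both analyses do not ask for a full dose. SAP 5.4: "The PK Analysis Set includes all participants in the FAS with at least 1 measurable postdose concentration data to provide interpretable results". Its parent set, in SAP 5.2: "The Full Analysis Set (FAS) includes all randomized participants who received at least 1 dose of study drug".

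SAP 6.5 says that PK summaries "will be based on the PK Analysis Set and presented by VIR-3434 treatment cohort and placebo, for each of Part A, B, C, and D". SAP 6.5.2 names one exclusion from the concentration summaries: "Anomalous concentrations identified as sampling errors by the clinical pharmacologist will be excluded from summaries but flagged in the listings". SAP 6.5.1 adds discretionary exclusions when λz or AUCinf is poorly estimated.

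Protocol 5.5 anticipates the event. It begins "Subjects who do not receive the full planned dose or discontinue due to an AE" and goes on to allow replacement, with the replacement given the same assignment and dose level. Neither document says whether the replaced subject's PK data stay in the cohort summary.

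**The concern.** The same subject is handled in two ways in adjacent sections. A subject who received part of the dose will normally have measurable concentrations and derivable parameters, so SAP 6.5.3 includes that subject while SAP 6.5.4 does not. With 6 active subjects per cohort, one low profile carries a sixth of the weight in the geometric mean.

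At stake is the accuracy of the reported cohort exposure. Serum PK parameters are a secondary endpoint in every part, and Protocol 2.3.2 gives PK data for further clinical development as one reason for the Part A dose range. For Part A SC, the exposure table and the proportionality analysis could also rest on different subjects with no note to say so. The sponsor is not blinded, so a rule fixed before database lock is better than a decision taken once the profile has been seen.

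**Working it through.** The plan states no figure for the effect of a dosing deviation, so there is none to reproduce.

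**Step 1. Does any rule remove a part-dosed subject from the cohort summaries?**

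| Place | Rule | Covers a part dose? |
|---|---|---|
| SAP 5.2, FAS | Randomized, at least 1 dose received | No |
| SAP 5.4, PK Analysis Set | FAS plus at least 1 measurable postdose concentration | No |
| SAP 6.5.1 | Discretionary exclusion for poor λz or extrapolated AUC above 20% | No; not tied to the dose received, and does not touch Cmax or AUClast |
| SAP 6.5.2 | Sampling errors excluded | No |
| SAP 6.5.3 | All with derivable parameters included | Keeps the subject |
| SAP 6.5.4 | Dosing deviations excluded | Yes, for dose proportionality only |

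**Step 2. Inputs for the size.**
- n = 6 active subjects per cohort: 1 of the 2 sentinels plus 5 of the remaining 6 (Protocol 2.4; 6:2 in Protocol Tables 1 and 2).
- n = 7 if the part-dosed subject is replaced and both are counted (Protocol 5.5).
- f = fraction of the dose received. The documents give none, so a range is shown.
- Assumption: exposure is proportional to the dose received.

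**Step 3. Shift in the geometric mean of Cmax, AUC or the concentration at a given time** (and of Clast, if the last measurable time is unchanged). One of n values is multiplied by f, so the geometric mean is multiplied by f^(1/n), and the shift is f^(1/n) - 1.

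| f | n = 6 |
|---|---|
| 0.90 | 0.90^(1/6) - 1 = -1.7% |
| 0.75 | 0.75^(1/6) - 1 = -4.7% |
| 0.50 | 0.50^(1/6) - 1 = -10.9% |
| 0.25 | 0.25^(1/6) - 1 = -20.6% |

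With a replacement also counted, f = 0.50 gives 0.50^(1/7) - 1 = -9.4%. A fall of exactly 10% with n = 6 needs f = 0.9^6 = 0.53. The arithmetic mean at f = 0.50 falls by 1 - 5.5/6 = 8.3%.

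**Step 4. Spread.** Assume a geometric CV of 30% (not in the documents). The log-variance is ln(1.09) = 0.086. One half-dosed subject among 6 adds (ln 2)²/6 = 0.080 to the expected sample variance. The geometric CV becomes √(exp(0.166) - 1), about 42%.

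**Step 5. Parameters that do not shift.** Under the same assumption Tmax, half-life and λz are unchanged. CL/F depends on the dose entered. With the actual dose it does not shift. With the planned dose, at f = 0.50 and n = 6, it rises by 2^(1/6) - 1 = 12.2%. The SAP does not say which is used.

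**Step 6. After the fix.** With the subject left out of the exposure summaries, the shift is 0 and n is 5, or 6 with a replacement.

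**The case against.** The strongest reply is that the two rules serve different purposes. The power model regresses a parameter on dose level, so a subject whose dose differs from that level breaks the covariate. A descriptive table of everything derivable has no such constraint. The study has no formal hypotheses, and no decision rule uses a cohort geometric mean. This stands as far as it goes: the sections differ but are not logically incompatible. It does not make a part-dosed Cmax or AUC representative of the cohort's dose.

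The size is modest. At a half dose the 10.9% shift is below one standard error of a 6-subject geometric mean, which is exp(√(0.086/6)) - 1 = 12.7% at the assumed 30% CV. At 90% of the dose it is negligible. This also stands, although the shift has a known direction and can be avoided.

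There are partial safeguards. The PK Analysis Set asks for interpretable results, individual parameters are listed with median and range, and important protocol deviations are listed by subject. These make an outlier visible but do not say whether it is counted.

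The mismatch between two analyses is certain only for Part A SC. No proportionality analysis is planned for the IV cohorts, although a stopped infusion (Protocol Appendix 8) is a plain route to a part dose. In those cohorts the issue is the summary alone.

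A reader might also infer that clearance and volume are computed at the nominal dose. The SAP says only that PK results are presented by cohort. Its sentence "Participants will be analyzed according to the treatment dose level they received" is in the safety section, and nothing equivalent is written for PK, so the point is open.

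**Conclusion.** The gap is real but small and conditional. As written, a part-dosed subject and any replacement both enter the cohort concentration, Cmax, Clast and AUC summaries, while the neighbouring section removes the part-dosed subject from dose proportionality. Per affected subject, the geometric mean moves by -1.7% to -20.6% for dose fractions from 0.90 to 0.25 with 6 active subjects. This rests on dose-proportional exposure and on fractions that are assumed. There is no effect if every subject receives the full dose.

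A reader might go further and infer that these summaries drive exposure-response work or dose selection. The documents do not support that. Protocol 10.5 relates PK parameters, not cohort means, to antiviral variables. Under Protocol 5.3, doses in this trial are proposed on safety and efficacy data and approved by the Safety Review Committee. SAP 3.5 places this analysis after all participants have finished. The consequence is limited to the accuracy of reported cohort exposure and its consistency with the proportionality analysis. It is a worthwhile clarification and does not threaten the trial's conclusions.

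**What to change.** In SAP 6.5.2 and 6.5.3, state that subjects with a dosing deviation are listed and flagged but excluded from the cohort summaries of concentration, Cmax, Clast and AUC, in line with 6.5.4. Keep their half-life and λz, subject to the quality criteria already in 6.5.1. Keep their CL, CL/F, Vz and Vz/F, calculated with the actual dose. Dropping the subject from every parameter would be too broad, because these remain valid.

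It would help to define dosing deviation, which 6.5.4 uses without a definition, and to say that a replaced subject follows the same rule.

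The cost is a sentence or two before database lock, and one fewer subject in a few summaries. That subject's data would remain visible in the listings.
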